### 2.7.4 Laboratory data

Laboratory parameters listed in [Table 2-1](#) will be presented graphically using boxplots of absolute change from baseline values by treatment group and visit. No summary by visit tables will be provided.

A summary table with number and percentage of subjects satisfying the criteria representing clinically relevant abnormalities defined in [Table 2-1](#) at any visit will be presented. A listing of subjects satisfying at least one criterion in [Table 2-1](#) at any visit will also be presented.

**Table 2-1 Clinically notable laboratory values**

Test	Critically Low	Critically High	Units
Hemoglobin	< 7.0	> 20.0	g/dL
White Cell Count	< 2.0	> 35.0	$\times 10^3/\mu\text{L}$
Platelets	< 50	> 1000	$\times 10^3/\mu\text{L}$
Glucose	< 40	> 500	mg/dL
Calcium	< 6.0	> 12.0	mg/dL
Phosphate	< 0.9		mg/dL
Sodium	< 120	> 160	mmol/L
Potassium	< 3.0	> 6.0	mmol/L
Magnesium	< 0.74	> 1.0	mmol/L
AST		41	U/L
ALT		45	U/L
Total bilirubin		21	$\mu\text{mol/L}$

## 2.7.5 Other safety data

### 2.7.5.1 ECG and cardiac imaging data

No applicable.

### 2.7.5.2 Vital signs

A listing of subjects satisfying at least one criterion in [Table 2-2](#) at any visit will be presented.

**Table 2-2 Clinically notable vital signs**

Variable	Category	Critical values
Systolic blood pressure (mmHg)	High	Either >180 with an increase from baseline >30 or >200 absolute
	Low	Either <90 with a decrease from baseline >30 or <75 absolute
Diastolic blood pressure (mmHg)	High	Either >105 with an increase from baseline >20 or >115 absolute
	Low	Either <50 with a decrease from baseline > 20 or <40 absolute
Pulse rate (bpm)	High	Either >120 with an increase from baseline of >25 or > 130 absolute
	Low	Either <50 with a decrease from baseline >30 or <40 absolute

## 2.8 Pharmacokinetic endpoints

Not applicable.

## 2.9 PD and PK/PD analyses

Not applicable.

## 2.10 Patient-reported outcomes

### Functional Reading Independence (FRI) Index

The FRI index is a new patient-reported outcome measure developed specifically for use in GA patients. The FRI index evaluates the level of independence patients have in performing everyday activities that require reading, such as writing a cheque or reading a prescription. Scores derived from the index range from 1 (unable to do) to 4 (total independence).

The composite score is the sum of the seven sub-questions.

If responses are missing for main questions or sub-questions, scores may be imputed based on the scoring for missing items algorithm provided in [Table 2-3](#) below.

**Table 2-3 Scoring Missing FRI Items**

Question or Sub-Question with Missing Data	Missing Response within Context of other Sub-Questions	Coding and Imputation

Main Questions 1–7	If missing main question and responses of “Yes” or “No” to sub-questions a-e...	Impute “Yes” to main question and score according to algorithm
	If missing main question and “Your vision” or “For other reasons” to sub-question g....	Impute “No” to main question and score according to algorithm
	If missing main question and no responses to any sub-questions...	Code as “missing”
Sub-questions a–c	If missing sub-questions a-c...	Code as “missing” and score according to algorithm
Sub-question d	If missing sub-question d and “No” response to all sub-questions a-c...	Impute “No” for sub-question d and score according to algorithm
Sub-question e	If “Yes” to performing activity and “missing” for sub-question e and no responses to sub-question f...	Impute “No” for sub-question e and score according to algorithm
	If “Yes” to performing activity and “missing” for sub-question e and response of “Some of the time”, “Most of the time” or “All of the time” to sub-question f...	Impute “yes” for sub-question e and score according to algorithm
Sub-question f	If “Yes” to performing activity, “Yes” to sub-question e and “missing” for sub-question f...	Impute “Some of the time” for sub-question f and score according to algorithm
Sub-question g	If “No” to main question and “missing” for sub-question g...	Impute “For other reasons” for sub-question g and score according to algorithm

### Visual Function Questionnaires (VFQ-25)

The VFQ-25 consists of a base set of 25 vision-targeted questions representing 11 vision-related constructs, plus an additional single-item general health rating question. The VFQ-25 sub-scales and composite scores and changes from baseline will be calculated and summarized by assessment visits. Each subscale score has a range of 0 to 100 inclusive and will be calculated from the re-scaled raw data as described in [Table 2-4](#). A missing response will not be re-scaled (except for the response to question 15c, see below, which will be re-set to 0 if the response to question 15b is 1).

**Table 2-4 Rescaling of VFQ-25 questions**

Answer to question	Rescaling for questions 1, 3, 4 and 15c	Rescaling for question 2	Rescaling for questions 5-14, 16 and 16a	Rescaling for questions 17-25
1	100	100	100	0

2	75	80	75	25
3	50	60	50	50
4	25	40	25	75
5	0	20	0	100
6	N/A	0	N/A*	N/A

Item 15c has four-response levels, but is expanded to a five-levels using item 15b.

Note: If 15b=1, then 15c should be recoded to "0"

If 15b=2, then 15c should be recoded to missing

If 15b=3, then 15c should be recoded to missing

[figure not shown]
\*Response choice "6" indicates that the person does not perform the activity because of non-vision related problems. If this choice is selected, the item is coded as "missing".

[figure not shown]
The subscale scores are then calculated according to [Table 2-5](#).

[figure not shown]
**Table 2-5 Questions contributing to VFQ-25 subscales**

Subscale	Questions
General vision	2
Ocular pain	4 and 19
Near activities	5, 6 and 7
Distance activities	8, 9 and 14
Social functioning	11 and 13
Mental health	3, 21, 22 and 25
Role difficulties	17 and 18
Dependency	20, 23 and 24
Driving	15c, 16 and 16a
Color vision	12
Peripheral vision	10

The composite score is the average of the 11 subscales shown in [Table 2-5](#). It will be set to missing if at least six of the subscales are missing.

[figure not shown]
### 3 Sample size calculation

Untreated control mean GA change at 48 weeks was assumed to be  $2.1 \text{ mm}^2$  with standard deviation (SD) =  $1.3 \text{ mm}^2$ . The following hypotheses are considered:

$$H0_L: \mu_L - \mu_C = 0, H_A L: \mu_L - \mu_C < 0$$

$$H0_H: \mu_H - \mu_C = 0, H_A H: \mu_H - \mu_C < 0$$

Where  $\mu_L$ ,  $\mu_H$  and  $\mu_C$  represent the unknown true mean GA change on FAF at 48 weeks in the GT005 low dose [REDACTED], GT005 high dose [REDACTED], and pooled untreated control, respectively.

Including the additional subjects that are already randomized to the high dose group (approximately 10 subjects) in Part 1, the overall sample size is approximately 202.

## 4 Change to protocol specified analyses

The Week 48 interim analysis was removed.

The Safety Analysis Set (SAF) was removed.

The estimand framework was simplified. Analysis for the primary endpoint was changed to MMRM.

Subgroup of interest is not applicable.

## 5 Appendix

Statistical methods are described in the main part of the clinical study report. This appendix provides further details on missing data imputation, statistical methods, and statistical derivation.

### 5.1 Imputation rules

The general approach to handling missing dates is shown below for dates of AEs, medical history diagnosis, and concomitant treatment. The imputation of missing dates for surgery or procedures will use the same rules as for concomitant treatment.

The detailed algorithms will appear in Programming Dataset Specifications.

For the purpose of date imputation, the treatment follow-up period date is defined as the last available visit date.

#### 5.1.1 AE date imputation

##### 5.1.1.1 Adverse event end date imputation

1. If the AE end date month is missing, the imputed end date should be set to the earliest of the (treatment follow up period date, 31DECYYYY, date of death, cut-off date if available).
2. If the AE end date day is missing, the imputed end date should be set to the earliest of the (the last visit date, last day of the month, date of death, cut-off date if available).
3. If AE year is missing or AE is ongoing, the end date will not be imputed.
4. In case the imputed AE end date is before AE start date, then use AE start date as imputed AE end date.

##### 5.1.1.2 Adverse event start date imputation

The following table explains the notation used in the logic matrix. Please note that **missing start dates** will not be imputed.

Day	Month	Year
-----	-------	------

Partial Adverse Event Start Date	Not used	MON	YYYY
Randomization Date	Not used	RANDM	RANDY

The following matrix explains the logic behind the imputation.

	MON MISSING	MON < RANDM	MON = RANDM	MON > RANDM
YYYY	(1)	(1)	(1)	(1)
MISSING	No convention	No convention	No convention	No convention
YYYY < TRTY	(2.a) Before Randomization	(2.b) Before Randomization	(2.b) Before Randomization	(2.b) Before Randomization
YYYY = TRTY	(4.a) Uncertain	(4.b) Before Randomization	(4.c) Uncertain	(4.c) After Randomization
YYYY > TRTY	(3.a) After Randomization	(3.b) After Randomization	(3.b) After Randomization	(3.b) After Randomization

Before imputing AE start date, find the AE start reference date.

1. If the (imputed) AE end date is complete and the (imputed) AE end date < randomization date then AE start reference date = min (informed consent date, earliest visit date).
2. Else AE start reference date = randomization date

Impute AE start date -

1. If the AE start date year value is missing, the date uncertainty is too high to impute a rational date. Therefore, if the AE year value is missing, the imputed AE start date is set to NULL.
2. If the AE start date year value is less than the randomization date year value, the AE started before randomization. Therefore:
  - a. If AE day and month are missing, the imputed AE start date is set to the mid-year point (01JulYYYY).
  - b. If AE month is missing but day is not missing, the observed start date will be used with month imputed as JulYYYY.
  - c. Else if AE month is not missing, the imputed AE start date is set to the mid-month point (15MONYYYY).
3. If the AE start date year value is greater than the randomization date year value, the AE started after randomization. Therefore:
  - a. If the AE day and month are missing, the imputed AE start date is set to the year start point (01JanYYYY).
  - b. If AE month is missing but day is not missing, the observed start date will be used with month imputed as JulYYYY.
  - c. Else if the AE month is not missing, the imputed AE start date is set to the later of (month start point (01MONYYYY), AE start reference date + 1 day).
4. If the AE start date year value is equal to the randomization date year value:
  - a. And the AE day and month are missing the imputed AE start date is set to the AE reference start date + 1 day.
  - b. If AE month is missing and day is not missing, the observed start date will be used with month imputed as the reference start month.

- c. Else if the AE month is less than the randomization month, the imputed AE start date is set to the mid-month point (15MONYYYY).
- d. Else if the AE month is equal to the randomization date month or greater than the randomization date month, the imputed AE start date is set to the later of (month start point (01MONYYYY), AE start reference date + 1 day).

If complete (imputed) AE end date is available and the imputed AE start date is greater than the (imputed) AE end date, then imputed AE start date should be set to the (imputed) AE end date.

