### **2.7.1 Adverse events (AEs)**

Only AEs that occurred during the study period (from the date of randomization to the end of study) will be summarized. AEs recorded after screening but before the date of randomization will be listed only.

**Treatment-emergent Adverse Event (TEAE):** An adverse event is considered treatment emergent if the start date/time of the event is on or after the date of randomization, irrespective of the treatment arm. The primary summaries of AEs will be based on TEAEs.

The number (and percentage) of subjects with AEs will be summarized separately for ocular (study eye and fellow eye) and non-ocular events by treatment group in the following ways unless otherwise specified:

- Overall summary of death, subjects with any AE, any severe AE, any study treatment-related AE, any surgical procedure related AE, any AE leading to study discontinuation, any serious AE (SAE), any study treatment-related SAE, any surgical procedure related SAE, any SAE leading to study discontinuation
- AEs by primary SOC and PT
- AEs related to study treatment by SOC and PT (separately for study eye and non-ocular)
- AEs related to surgical procedure by SOC and PT (separately for study eye and non-ocular)
- SAEs by primary SOC and PT

- SAEs related to study treatment by SOC and PT (separately for study eye and non-ocular)
- SAEs related to surgical procedure by SOC and PT (separately for study eye and non-ocular)

A subject with multiple adverse events within a primary SOC is only counted once towards the total of the primary SOC.

All AEs, deaths, and SAEs (including those from the pre- and post-treatment periods) will be listed and those collected after the use of alternative GA therapies/medications, or during the pre-treatment, post-study period will be flagged. In addition, subjects who are not receiving treatment due to surgical procedure-related AEs will be listed separately by treatment group.

The MedDRA version used for reporting the AEs will be described in footnote.

For the legal requirements of ClinicalTrials.gov and EudraCT, two required tables on “on-treatment/treatment emergent” adverse events which are not serious adverse events with an incidence greater than 2% (or other cutting point as appropriate) and on “on-treatment/treatment emergent” serious adverse events and SAE suspected to be related to study treatment will be provided by system organ class and preferred term on the safety set population (i.e., the FAS of this study).

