#### 5.1.2.2 Concomitant treatment start date imputation

The following table explains the notation used in the logic matrix. Please note that **missing start dates** will not be imputed.

	Day	Month	Year
Partial CMD Start Date	Not used	MON	YYYY
Randomization Date	Not used	RANDM	RANDY

The following matrix explains the logic behind the imputation.

	MON	MON < RANDM	MON = RANDM	MON > RANDM
	MISSING			
YYYY	(1)	(1)	(1)	(1)
MISSING	Uncertain	Uncertain	Uncertain	Uncertain
YYYY < TRTY	(2.a)	(2.b)	(2.b)	(2.b)
	Before Randomization	Before Randomization	Before Randomization	Before Randomization
YYYY = TRTY	(4.a)	(4.b)	(4.a)	(4.c)
	Uncertain	Before Randomization	Uncertain	After Randomization
YYYY > TRTY	(3.a)	(3.b)	(3.b)	(3.b)
	After Randomization	After Randomization	After Randomization	After Randomization

If the CM start date year value is missing, the imputed CM start date is set to one day prior to randomization date.

If the CM start date year value is less than the randomization date year value, the CM started before randomization. Therefore:

- a. If the CM day and month are missing, the imputed CM start date is set to the mid-year point (01JulYYYY).
- b. If CM month is missing but day is not missing, the observed start date will be used with month imputed as JulYYYY.
- c. Else if the CM month is not missing, the imputed CM start date is set to the mid-month point (15MONYYYY).

If the CM start date year value is greater than the randomization date year value, the CM started after randomization. Therefore:

- a. If the CM day and month are missing, the imputed CM start date is set to the year start point (01JanYYYY).
- b. If CM month is missing but day is not missing, the observed start date will be used with month imputed as JanYYYY.
- c. Else if the CM month is not missing, the imputed CM start date is set to the month start point (01MONYYYY).

If the CM start date year value is equal to the randomization date year value:

- a. And the CM day and CM month are missing or the CM day is missing and CM month is equal to the randomization date month, then the imputed CM start date is set to one day prior randomization date.
- b. Else if the CM month is less than the randomization date month, the imputed CM start date is set to the mid-month point (15MONYYYY).
- c. Else if the CM month is greater than the randomization date month, the imputed CM start date is set to the month start point (01MONYYYY).

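### SAP 5.1.1.2 gives conflicting rules for AEs with a known start day but missing month, and the text rule can date a post-randomisation AE before randomisation

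*SAP*

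**What the plan says.** SAP 2.7.1 ties treatment emergence to one date: "An adverse event is considered treatment emergent if the start date/time of the event is on or after the date of randomization". It tabulates only AEs between randomisation and end of study. AEs dated after screening but before randomisation are listed only. TEAE frequency through Week 96 is a secondary endpoint.

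SAP 5.1.1.2 imputes incomplete start dates from a reference date. This is the earlier of consent and first visit if the AE ended before randomisation; otherwise "Else AE start reference date = randomization date". The rules that matter here are:

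- **Rule 1 (year missing):** "if the AE year value is missing, the imputed AE start date is set to NULL".
- **Rule 3.b (year after randomisation year, day known, month missing):** "If AE month is missing but day is not missing, the observed start date will be used with month imputed as JulYYYY".
- **Rule 4.a (randomisation year, day and month missing):** "the imputed AE start date is set to the AE reference start date + 1 day".
- **Rule 4.b (randomisation year, day known, month missing):** "the observed start date will be used with month imputed as the reference start month".
- **Rules 3.c and 4.d (month known):** the later of the first of the month and the reference date plus one day.
- **Closing rule:** a start later than a complete or imputed end date is moved back to that end date.

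SAP 5.1.1.1 imputes no end date for an ongoing AE or one whose year is missing. For a later-year medication with month missing and day known, SAP 5.1.2.2 differs from rule 3.b: "the observed start date will be used with month imputed as JanYYYY".

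The matrix in 5.1.1.2 marks the day as unused. It sends every missing-month record to 4.a in the randomisation year and 3.a in a later year.

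**The concern.** The imputed start decides whether an AE enters the main safety tables. Rules 3.c and 4.d contain a floor that keeps a possibly post-randomisation AE on the post-randomisation side, and 4.a has the same effect. Text 4.b has no such floor, so a record with more date information can leave the tables while a record with less stays in. Text 3.b repeats the July of rule 2.b, although 3.a and the medication rule both use January, and it has no upper limit. Rule 1 stops at NULL without saying what follows.

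The matrix then contradicts the text for the same records. Two programmers who each followed 5.1.1.2 faithfully could produce different TEAE counts.

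**Working it through.** The plan states no figure on this point, so there is none to reproduce. The check applies the text rules literally. Calendar dates are illustrative, not from the documents.

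**Rule 4.b.** Randomised 20 March 2022, surgery 18 April, AE truly starting 5 May and ending 12 May, recorded as day 5, month unknown, 2022.

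1. The AE ended after randomisation, so the reference date is 20 March 2022.
2. Text 4.b: day 5 in the reference month gives 5 March 2022, which is 20 − 5 = 15 days before randomisation. Not a TEAE; listed only.
3. Closing rule: 5 March is not later than 12 May, so nothing changes. This rule only moves a start back, never forward.
4. Matrix, or text with the day also unknown (4.a): 20 March + 1 day = 21 March 2022. A TEAE.

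If the recorded day were 25, 4.b would give 25 March and the AE would be kept. The misdating needs a recorded day earlier than the randomisation day of the month.

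**Frequency within the pattern.** Assume a 365-day year, every randomisation date, and every later onset in that year equally likely. With onset from the day after randomisation there are 365 × 364 / 2 = 66,430 pairs.

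| First possible onset after randomisation | Pairs | Dated before randomisation | Impossible date (e.g. 31 February) |
|---|---|---|---|
| 1 day | 66,430 | 44.1% | 1.6% |
| 28 days | 56,953 | 44.1% | 1.9% |
| 56 days | 47,895 | 44.3% | 1.9% |

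**Rule 3.b.** Same subject, end of study 19 February 2024, AE truly starting 10 January 2024, recorded as day 10, month unknown, 2024.

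1. If ongoing, no end date is imputed. Text 3.b gives 10 July 2024, after end of study.
2. If it ended on 30 January 2024, the closing rule resets the start to 30 January 2024 and the AE stays inside the study period.
3. January imputation would give 10 January 2024. Rule 3.a would give 1 January 2024.

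For an AE with no end date in the calendar year the subject leaves, the share of the 31 possible July dates after end of study is 31/31 = 100% if the subject leaves by 30 June, 16/31 = 52% on 15 July, and 0% from 1 August. Over all pairs of 2024 end-of-study date and earlier onset in that year, it is 28.8%.

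**Rule 1.** A missing year with a known end date after surgery still gives NULL. Nothing in 2.7.1 or 5.1.1.2 classifies a NULL start; the matrix says only that there is no convention.

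**Matrix labels for known months.** Cells 2.b and 3.b correspond to text 2.c and 3.c. Cell 4.b (month before randomisation) corresponds to text 4.c. Cell 4.c (same or later month) corresponds to text 4.d. The matrix rows use TRTY, whereas the notation table defines RANDY.

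**The case against.** The strongest reply is that the matrix already gives acceptable answers. Read that way, the example AE is dated 21 March and July is never reached. SAP 5.1 also defers detailed algorithms to the Programming Dataset Specifications, which are not among the documents and may settle the matter. This reply stands in part: 4.b and 3.b do harm only if the text prevails. But 5.1.1.2 does not say which prevails, and a specification should implement the SAP rather than choose between two versions of it.

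The second reply is rarity. A known day with an unknown month is an unusual record. The protocol asks about AEs at every visit (7.4.2), requires SAE and AESI reports within 24 hours (8.5.1), and provides for edit checks and queries (12.1). This stands, and it limits the practical size.

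Four stronger readings are tempting but unsupported:

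- **That 3.b removes TEAE status.** The TEAE definition has no upper bound, so a July date still meets it. Only the sentence limiting summaries to the study period could exclude the AE, and only when it has no complete or imputed end date.
- **That every missing-year AE is dropped.** The SAP is silent on NULL starts; exclusion is an inference.
- **That the rules selectively lose post-surgery AEs and so favour GT005.** They depend on randomisation and apply equally to untreated controls. No between-arm bias is shown.
- **That 44% of AEs are lost.** The figure applies only to truly post-randomisation AEs in the randomisation year with day known and month missing.

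**Conclusion.** The point holds as an internal contradiction with one clear error. Text 4.b lacks the floor used in 3.c and 4.d, and can turn a possible TEAE into a listing-only event that 4.a would have counted. Within its pattern the misdating rate is about 44%, assuming uniform dates.

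The 3.b problem is narrower: no complete or imputed end date, and a subject whose study ends before the imputed July date. How many subjects leave before July of a later year is not in the documents. The early termination described in SAP 1 makes this plausible but does not establish it. Rule 1 is an unspecified case, not a stated exclusion.

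The expected effect on the tables is small, because such records are probably few. They remain visible in the listings. It is still worth correcting: TEAE frequency is a secondary endpoint, the 4.b error under-counts AEs, and the SAP is dated before final database lock.

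**What to change.** In SAP 5.1.1.2, and in the programming specification to match:

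- **(a) Rule 4.b:** use the later of the imputed date and the AE start reference date plus one day. An AE that ended before randomisation is still held there by the closing rule.
- **(b) Rule 3.b:** use January, as in 5.1.2.2. Cap any imputed start at the end-of-study date, and replace an impossible date with a valid day.
- **(c) Rule 1:** state that an AE with a missing start year counts as treatment-emergent unless it ended before randomisation.
- **(d) Matrix:** route day-known, month-missing records explicitly to 3.b and 4.b; or delete those two rules and use 3.a and 4.a for every missing month, which discards the known day but avoids impossible dates. Correct the known-month labels to 2.c, 3.c, 4.c and 4.d, and replace TRTY with RANDY.

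The cost is a few lines of text and code. Some AEs that truly began before randomisation will be counted as TEAEs, which is the conservative direction for safety. The cap in (b) should not be applied to AEs known to have begun after the study, which 2.7.1 lists and flags separately.
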